Abbreviations: AD = Atopic Dermatitis; BSA = Body Surface Area; CBC = Complete Blood Count; COVID-19 = coronavirus disease 2019; CXR = Chest X-ray; DLCO = Diffusion Capacity; DLQI = Dermatology Life Quality Index; EASI = Eczema Area and Severity Index; ECG = electrocardiogram; eCRF = Electronic Case Report Form; eGFR = estimated Glomerular Filtration Rate; FEV1 = Forced Expiratory Volume in 1 second; FVC = Forced Vital Capacity; FSH = Follicle Stimulating Hormone; HBcAb = Hepatitis B core antibody; HBsAb = Hepatitis B surface antibody; HBsAg = Hepatitis B surface antigen; HCV = Hepatitis C virus; HIV = Human Immunodeficiency virus; ICF = Informed Consent Form; INR = international normalized ratio; IRT = Interactive Response Technology; LH = Luteinizing hormone; NRS = Numerical Rating Scale; PA = Posteroanterior; POEM = Patient Oriented Eczema Measure; PPE = Personal Protective Equipment; PT = prothrombin time; RT-PCR = Reverse transcriptase polymerase chain reaction; SAE = Serious Adverse Event; SARS-CoV-2 = severe acute respiratory syndrome coronavirus 2; TB = Tuberculosis; UA = urinalysis; vIGA-AD = validated Investigator Global Assessment scale for Atopic Dermatitis; WOCBP = Women of Childbearing Potential.

Table 2-2: On-treatment Procedural Outline (IM018005)

Procedure	Day 1 ^a (Rand)	Day 8 W1 (± 1 days)	Day 15 W2 (± 3 days)	Day 29 W4 (± 3 days)	Day 57 W8 (± 3 days)	Day 85 ^a W12 (± 3 days)	Day 113 (EOT) W16 (± 3 days)	Notes
Administrative and Historical Assessments								
Inclusion/Exclusion Criteria	X							Review of inclusion/exclusion criteria that are specified on or defined relative to the randomization day
Randomization via IRT	X							
Disease/Efficacy Assessment								
EASI	X	X	X	X	X	X	X	EASI at baseline must be ≥ 16 (prior to randomization).
vIGA-AD	X	X	X	X	X	X	X	
BSA Assessment	X	X	X	X	X	X	X	
Pruritus and Sleep Quality NRS	X	X	X	X	X	X	X	Will be collected daily in an electronic diary – represents preceding 24 hours. Data will be collected at each specified visit.
DLQI	X	X	X	X	X	X	X	Data will be collected at each specified visit.
POEM	X	X	X	X	X	X	X	
PGI-S	X	X			X		X	
PGI-C		X			X		X	
Pulmonary Function Test				X			X	FEV1, FVC & DLCO may be collected within a window of ± 5 days of visit.
Visual Acuity Testing and Optical Coherence Tomography					X		X	May be collected within a window of ± 7 days of visit.
Safety Activities								
Body Weight	X						X	

Table 2-2: On-treatment Procedural Outline (IM018005)

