Abbreviations: AD = Atopic Dermatitis; AE = Adverse Event; BSA = Body Surface Area; CBC = Complete Blood Count; DLQI = Dermatology Life Quality Index; EASI = Eczema Area and Severity Index; ECG = electrocardiogram; eGFR = estimated Glomerular Filtration Rate; EOS = end of study; FSH = Follicle Stimulating Hormone; ICF = Informed Consent Form; IRT = Interactive Response Technology; LH = Luteinizing hormone; NRS = Numerical Rating Scale; PGI-C=Patient Global Impression of Change; PGI-S=Patient Global Impression of Severity; PK = pharmacokinetics; POEM=Patient Oriented Eczema Measure; SAE = serious adverse event; SARS-CoV-2 = severe acute respiratory syndrome coronavirus 2; UA = urinalysis; vIGA-AD = validated Investigator Global Assessment scale for Atopic Dermatitis; WOCBP = women of childbearing potential.

When multiple assessments are conducted at a single visit, the following is the order in which they should be performed:

- 1) Safety assessments (eg, vitals, electrocardiograms [ECG], adverse events [AEs])
- 2) Laboratory tests (eg, safety laboratory tests, pharmacokinetic assessments, biomarker assessments)
- 3) Clinical efficacy assessments
- 4) Treatment dosing

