7.7.3 Use of Concomitant Emollient

Application of fixed doses of an additive-free, basic bland emollient twice-daily for ≥ 7 days before baseline visit and for the duration of the study is required.

Note: On study visit days, showering or bathing is permitted prior to attending the study visit, but participants must not moisturize or apply emollient. The additive-free, basic bland emollient is allowed after the visit.

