9 STUDY ASSESSMENTS AND PROCEDURES

- Study procedures and timing are summarized in the Schedule of Activities.
- Protocol waivers or exemptions are not allowed.
- All immediate safety concerns must be discussed with the Sponsor immediately upon occurrence or awareness to determine if the participant should continue or discontinue treatment.
- Adherence to the study design requirements, including those specified in the Schedule of Activities, is essential and required for study conduct.
- All screening evaluations must be completed and reviewed to confirm that potential participants meet all eligibility criteria before randomization. The investigator will maintain a screening log to record details of all participants screened and to confirm eligibility or record reasons for screening failure, as applicable.
- Procedures conducted as part of the participant's routine clinical management (eg, blood count) and obtained before signing of informed consent may be utilized for screening or baseline purposes provided the procedure meets the protocol-defined criteria and has been performed within the timeframe defined in the Schedule of Activities.

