9.8 Biomarkers

The objectives of the biomarker work are to confirm target engagement for BMS-986166 (S1PR) and branebrutinib (BTK), and to understand the biological consequences of blocking these pathways in AD participants.

[REDACTED]

[REDACTED] Samples may also be used to build or improve assays related to the above questions. The biomarker approaches for this study are discussed in the following subsections in greater detail, and will focus on leukocyte counts and inflammatory signaling molecules in blood (eg, Th2 cells and eosinophils in whole blood, RAST, Serum IgE, and cytokines), gene expression analysis in blood and tissue, pathologic analyses of skin biopsies (eg, histology, lymphocyte and neutrophil infiltration, eosinophils, mast cells), and proteomic/gene expression analyses of skin tape stripping samples. Where possible, blood and tissue samples will be collected at multiple timepoints to facilitate longitudinal analyses.

The collection of the stratum corneum, the uppermost layer of the epidermis, by tape-stripping offers the advantage of obtaining skin samples in a simple and noninvasive manner. This technique has been used to determine different skin biomarkers such as interleukin (IL)-1 cytokines, enzymes, lipids, and filaggrin degradation products. Details on the use of tape stripping procedures in AD patients as well as the downstream biomarker analyses^{128,129,130,131} will be provided in the Study Laboratory Manual.

Measurements may also include, but are not limited to, assessments of SARS-CoV-2 serologic status. Serum will be collected at baseline and end of study for optional measurements of SARS-CoV-2 serology (anti-SARS-CoV-2 IgM and/or IgG and/or IgA). Further details of sample collection and processing for blood, serum, and skin biopsies will be provided to the site in the Study Laboratory Manual.

Table 9.8-1: Biomarker Sampling Schedule All Participants (IM018005)

Study Day of Sample Collection	Serum Biomarkers ^a	Whole Blood for BTK Occupancy	Whole Blood Total BTK pBTK	Whole Blood DNA	Whole Blood Epigenetic Analyses ^b	Whole Blood RNA (PAXgene) ^c	Flow Cytometry	Skin Tape Stripping	Skin Biopsy (optional)	SARS-CoV-2 Serology
Day 1	X	X	X	X	X	X	X	X	X	X
Day 8	X	X	X			X				
Day 29	X	X	X		X	X	X	X		
Day 85	X	X	X			X				
Day 113 / EOT	X	X	X		X	X	X	X	X	
Follow Up - Day 127	X	X	X		X	X	X			
Follow Up - Day 169	X	X	X		X	X	X			X
Study Withdrawal										X

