9.8.2 Additional Exploratory Biomarkers

As current scientific literature and internal BMS research suggests that BTK and S1P signaling may impact many overlapping, complementary immunological processes and immune cell types, exploratory analyses will be performed with the goal of producing the same data outputs whenever possible. This approach will maximize the translational value of the dataset, ensuring that this study will advance understanding of the field regardless of the efficacy seen in this study, and thus provide value to the AD patient community.

Cellular analyses will include, but may not be limited to, skin and blood analysis of Th2 cells and other T-cells subsets, B-cells, eosinophils, basophils, mast cells, neutrophils, myeloid cells, and innate lymphoid cells. A combination of techniques including gene expression analyses, ELISA or other protein measurements for serum IgE and cytokines, proteomic/gene expression analyses of skin tape stripping samples, autoantibodies, and clinical chemistry tests such as RAST and serum surrogates of mast cell activation will be used to build a comprehensive picture of the response of AD participants to BTK and S1P inhibition. Genetic analyses will include, but are not limited to mutations in the Filaggrin gene (FLG), with FLG potentially informing on disease mechanisms relevant to pediatric vs. adult AD in particular.^{24,133}

Skin punch biopsies will be optional but strongly encouraged, with a minimum goal of 12 biopsies per group, since they are critical to a full understanding of response to these therapies in AD participants. Looking to future studies, having as many skin samples as possible will also allow for greater understanding of which tissue measures may have viable blood/serum surrogates and what can only be assessed accurately from biopsies. Immune cell trafficking, expected to be one of the major phenomena affected by BMS-986166, is expected to fall into the category of those requiring tissue assessment. Skin punch biopsies will be taken at baseline and at end of treatment, and either frozen, placed in formalin, or sent into an equivalent process as appropriate for the experimental end use of the material (ie, separate processing for RNA extraction). Details for the biopsy procedures will be provided in the Study Laboratory Manual.

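### The visit order in Section 2 puts tape stripping and biopsy ahead of EASI, vIGA-AD and BSA scoring, and on Day 1 ahead of the eligibility check

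*Combined protocol and SAP*

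**What the plan says.** At the end of Section 2, for visits with several assessments, the protocol states that "the following is the order in which they should be performed". The steps are safety assessments, then "Laboratory tests (eg, safety laboratory tests, pharmacokinetic assessments, biomarker assessments", then "Clinical efficacy assessments", then dosing. Section 9 gives the Schedule binding force: "Adherence to the study design requirements, including those specified in the Schedule of Activities, is essential and required for study conduct".

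The on-treatment schedule (Table 2-2) sends biomarker collection to Table 9.8-1, which has columns for skin as well as blood. Tape stripping is marked on Days 1, 29 and 113 for all participants. Biopsy is marked optional on Days 1 and 113, and Section 9.8.2 says "Skin punch biopsies will be taken at baseline and at end of treatment". Section 9.8 names "proteomic/gene expression analyses of skin tape stripping samples" as part of the biomarker work.

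For Day 1, Table 2-2 requires that "EASI at baseline must be ≥ 16 (prior to randomization". Section 6.1 sets the screening threshold at 12 and repeats the vIGA-AD and BSA criteria at baseline.

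**The concern.** The primary endpoint is percent change in EASI from baseline to Week 16, so Days 1 and 113 are the two readings it depends on. They are also the two visits at which both kinds of skin sampling are scheduled. Read literally, the order has skin stripped or punched and only afterwards rated for erythema, papulation and excoriation.

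The more concrete problem is on Day 1. Someone who enters that visit on the screening result has not yet met the baseline EASI criterion, and the order places the sampling before the reading that decides it. A person who consented to biopsy could undergo an invasive procedure and then be turned away, leaving a sample with no use in the trial.

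**Working it through.** **Can any other text move skin sampling after scoring?**

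- Section 9.6 requires biomarker samples to be predose. Efficacy scoring is also predose, so the rule is met whichever comes first.
- Section 9.5.1 lets other procedures shift so that PK samples are taken on time. It does not ask for skin to be scored before it is sampled.
- Section 9.1.1 puts vIGA-AD before EASI and does not mention skin sampling.
- Sections 9.8 and 9.8.2 leave procedures and windows to a laboratory manual that is not among the documents.

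Nothing in the protocol exempts tape stripping or biopsy from step 2.

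**Day 1 eligibility (Section 6.1)**

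| Criterion | Screening | Baseline |
|---|---|---|
| EASI | ≥ 12 | ≥ 16 |
| vIGA-AD | ≥ 3 | ≥ 3 |
| BSA | ≥ 10% | ≥ 10% |

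A participant screened with EASI from 12 to below 16 passes screening and must score higher on Day 1 to qualify. All three criteria can be met at screening and missed on Day 1. The documents give no rate for this.

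**Reach.** About 150 participants are to be randomized, all scheduled for tape stripping. The biopsy goal is at least 12 per group. If that counts participants, it is 12 × 5 = 60, and 60/150 = 40%. People sampled and then found ineligible would be additional to these.

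**Illustrative size of scoring noise.** The documents do not say how sampling alters a score. Assume one clear region is re-scored with area score 1 and one sign at 1, the lowest non-zero values in Appendix 9.

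- EASI contribution = sign × area score × region multiplier.
- Head/neck: 1 × 1 × 0.1 = 0.1 points. Lower limbs: 1 × 1 × 0.4 = 0.4 points.
- At a baseline EASI of 16: 0.1/16 = 0.6 and 0.4/16 = 2.5 percentage points of percent change.
- With the sign at 2, the upper end doubles to 0.8 points, or 5 percentage points.
- A harsher assumption is a half-point rise in one sign over fully involved lower limbs: 0.5 × 6 × 0.4 = 1.2 points, or 7.5 percentage points.

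An upward error at baseline makes percent improvement look larger and one at Week 16 makes it look smaller, so the two partly offset.

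**Effect on power.** Section 10.1 gives difference 30, SD 43, one-sided alpha 0.05, and power of 84% at 30 per group and 78% at 25.

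- Noncentrality at n = 30: 30 / (43 × √(2/30)) = 2.70. Power is 85.5% by the normal approximation and 84.7% by the t distribution.
- At n = 25: 79.4% and 78.4%. The plan's figures reproduce.

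Now add noise with an SD equal to the whole assumed shift, at n = 30, normal approximation:

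| Added SD | Total SD | Power | Loss (points) |
|---|---|---|---|
| 0 | 43.00 | 85.5% | – |
| 2.5 | √(43² + 2.5²) = 43.07 | 85.4% | 0.1 |
| 5 | √(43² + 5²) = 43.29 | 85.1% | 0.4 |
| 7.5 | √(43² + 7.5²) = 43.65 | 84.5% | 0.9 |

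**The case against.** The case for leaving the text alone has several parts.

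- **Unseen manual.** The laboratory manual may already separate the steps, so what sites do cannot be settled from the documents. That stands. A manual that did so would still depart from the protocol's order, and the two should agree.
- **Incomplete list.** The Section 2 list says should, and it does not mention eligibility review or randomization, which have their own rows in Table 2-2. It is therefore not a full Day 1 sequence. This is fair, but nothing else supplies the missing sequence, and Section 9 makes the Schedule binding.
- **Scoring rules.** Section 9.1.2 and Appendix 9 rate the average intensity of inflamed lesions. A trained assessor may ignore a known procedure mark, and a small site hardly moves a regional average. This stands and is why the noise figures are only illustrative.
- **Consent.** Biopsy is optional and separately consented. That limits who is exposed but does not justify sampling before eligibility is known.

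It would also be a mistake to lean on the rule that, before a visit, "participants must not moisturize or apply emollient". Section 7.7.3 gives no reason for it, and it could equally protect the tape-strip samples.

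Three stronger readings are tempting and are not supported:

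- **Changed responder status in nearly clear participants.** At baseline EASI 16 the EASI-50 cut is 8, and adding 0.1 to 0.8 points to a near-zero score does not approach it. vIGA-AD is a global rating without regions, Appendix 8 disregards excoriations, and a move from 0 to 1 is still a response.
- **Lesional tape stripping.** Section 9.8.1 refers to tissue readouts in AD lesions, but the tape-strip site is not stated.
- **Bias between arms.** The order is the same in every blinded arm, and nothing in the documents points to a differential effect.

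**Conclusion.** The point holds as a sequencing defect. As written, the protocol has skin sampled before EASI, vIGA-AD and BSA are scored at baseline and Week 16 (and, for tape stripping, at Day 29), and on Day 1 before three eligibility criteria are checked.

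The main consequence is avoidable skin sampling, including biopsy, of people who then fail Day 1. This follows from the text and needs no assumption about effect size, though its frequency is unknown. The secondary consequence is small, non-differential noise in the scores. On the base illustration it is 0.1 to 0.4 EASI points with a power loss of at most about 0.1 percentage point; even the harshest assumption above costs less than 1 point. Sample size and the stated power need no change. The conclusion rests on reading biomarker assessments in Section 2 to include the skin columns of Table 9.8-1, which is how the protocol itself classifies them.

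**What to change.** Amend the Section 2 list to read, in substance: safety assessments; blood and other laboratory tests, after the ECG as now; vIGA-AD, then EASI and BSA; on Day 1, confirmation that the baseline criteria are met; tape stripping and, where consented, biopsy; dosing. Add a footnote to Table 9.8-1 that skin samples are taken after scoring and before dosing, and align the laboratory manual.

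The predose rule in Section 9.6 is still met and PK timing is untouched. The patient questionnaires need no new rule. The cost is one reordered list, one footnote and one line in the manual, with no added procedure, staff or visit.

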3 INTRODUCTION

IM018005 is a Phase 2 study to assess the clinical benefit provided by each of 3 dose levels of BMS-986166, a modulator of sphingosine-1-phosphate receptor 1 (S1PR1), and of a single dose level of branebrutinib (an inhibitor of Bruton Tyrosine Kinase [BTK]) in participants with moderate-to-severe atopic dermatitis (AD).

Interventions that are safe and highly effective in a large majority of AD patients with moderate or severe disease remains an unmet medical need (Section 3.1.1). Despite the recent approval of dupilumab (anti-interleukin-4 receptor alpha monoclonal antibody) for the treatment of AD, after 16 weeks of treatment, approximately 40% of patients with moderate or severe AD, demonstrated a reduction of the Investigators' Global Assessment (IGA) to either 1 (almost clear) or 0 (clear). The substantial biological heterogeneity of AD warrants development of new medications acting through different mechanisms to treat patients, so that all may achieve remission or near-remission.

Signals transduced by receptors for sphingosine-1-phosphate (S1P) and by BTK are implicated in the pathobiology of AD (Section 3.1.2), making these pathways attractive targets for potential AD therapies.

BMS-986166 and branebrutinib demonstrated satisfactory safety, tolerability, pharmacokinetics (PK), and pharmacodynamics (PD) in Phase 1 clinical studies following extensive and promising nonclinical evaluations (Section 3.2). Thus, they are being evaluated in this Phase 2 study for their initial safety and efficacy in participants with moderate or severe AD.

3.1 Study Rationale

3.1.1 Disease Rationale

AD is one of the most common inflammatory skin diseases, affecting 3% to 10% of the US population.¹ Worldwide, it affects up to 20% of children and 3% of adults, with higher prevalence in younger children (ages 6 years to 7 years as compared with ages 13 years to 14 years) and also in some countries which have emerged as regions of relatively high prevalence.² In the majority of cases, AD has an onset before age 5 years, and prevalence data in children show a slight female to male preponderance (1.3 to 1).³ Persistent AD may be present in approximately 50% of patients diagnosed with atopic dermatitis during childhood.^{4,5} Of those affected, about 40% have moderate-to-severe disease.⁶ Beyond the characteristic skin pathology, AD is associated with increased anxiety, depression, sleep disorders, reduced productivity, and impaired activity – all of

[figure not shown]
approximately equivalent magnitudes to those observed in psoriasis.⁷ Patients with AD have increased risk of other atopic disorders, including asthma, allergic rhinitis, and chronic sinusitis with nasal polyposis.^{8,9,10} Taken together, the burdens of AD resulted in an estimated > \$5B in societal costs in 2016.¹¹

A multiplicity of factors, including epidermal barrier defects, dysregulation of innate immune responses, and altered Type 2 immunity, are implicated in the pathogenesis of AD, culminating in an inflammatory response involving multiple cell types, cytokines, and chemokines. The epidermis of patients with AD is characterized by a genetically impaired skin barrier function with increased transepidermal water loss. These abnormalities may be present at birth and predict the development of AD in the first year of life.¹² Higher levels of transepidermal water loss in patients with AD have been associated with greater disease severity.^{13,14} Enhanced allergen/antigen penetration through an impaired skin barrier resulting in a type 2 helper T-lymphocyte (Th2)-type milieu has been proposed as a critical link between the primary barrier defect in patients and Th2 polarization.¹⁵ Th2 differentiation of naive CD4+ T-cells predominates in AD causing an increased production of interleukins (IL), primarily IL-4, IL-5, and IL-13 (Figure 3.1.1-1), which then leads to an increased level of immunoglobulin E (IgE), and corresponding inhibition of type 1 helper T-lymphocyte (Th1) differentiation. In 80% of AD patients, the disease is associated with hypersensitivity to environmental or food allergens, increased specific serum IgE levels, and eosinophilia.^{16,17} Thus, AD is often part of (even the first manifestation of) a multi-system, Th2-dependent disease constellation that can include allergy, elevated IgE, and asthma.^{18,19,27} The barrier defects, other genetic and environmental factors, and exaggerated Th2 biology also involve activation of dermal keratinocytes and Langerhans cells, accompanied by in situ lymphocyte proliferation and activation – potentially accompanied by allergic phenomena in many cases²⁰ and possibly immune-mediated phenomena in a fraction of cases.²¹ This pathobiology further worsens barrier function and causes the chronic, self-sustaining syndrome of skin rash, pruritus, xerosis, and gram-positive skin dysbiosis that imposes the personal and societal burdens summarized above (Figure 3.1.1-1).

Until recently, treatment for moderate or severe AD involved hydration of the skin, and/or application of topical treatments such as glucocorticoids, calcineurin inhibitors, phosphodiesterase 4 (PDE4) inhibitors, tar, vitamin D, or dilute bleach. Severe, complex, or refractory cases invoked wet-wrap dressings, phototherapy, or systemic treatment with glucocorticoids, cyclosporine, and azathioprine -- for most patients, these approaches were, at best, partially satisfactory.¹⁰ More recently, biologic and small molecule therapies have proven to be promising investigational treatments for AD (Figure 3.1.1-1).²² In particular, the recent European Medicines Agency (EMA) and FDA approvals of dupilumab (anti-IL-4R α monoclonal antibody) represent a significant advance for AD patients.²⁹ Nevertheless, AD exhibits biological and clinical heterogeneity,^{23,24} and new medications employing different mechanisms are needed to provide a complete treatment armamentarium; indeed, the placebo-adjusted fraction of patients with moderate or severe AD demonstrating a reduction of Investigators' Global Assessment (IGA) to either 1 (almost clear) or

0 (clear) after 16 weeks of dupilumab treatment is only ~36%.^{25,26} Furthermore, dupilumab requires periodic injections which may be associated with inconvenience, discomfort, and injection-site reactions. New treatments for moderate and severe AD thus still represent a clear unmet need.

Figure 3.1.1-1: Schematic of Selected Immune Mechanisms in Atopic Dermatitis

Abbreviations: DC = dendritic cell; IgE = immunoglobulin E; IL = interleukin; ILC2 = type 2 innate lymphoid cell; LC = Langerhans cell; *S. aureus* = Staphylococcus aureus; TSLP = thymic stromal lymphopoietin. Schematic model of interplay between microbiome, skin barrier, and immunity in atopic dermatitis highlighting targets of novel biologic agents.²²

